4.5.3 Labeling

Labels for the investigational product will be prepared in accordance with Good Manufacturing Practice and local regulatory guidelines. Label text will be translated into local languages, as required.

4.5.4 Storage

Investigational product is to be stored at 2 to 8°C (36 to 46°F).

4.5.5 Treatment Compliance

Investigational product is administered by study site personnel, who will monitor compliance.

4.5.6 Accountability

The investigator's or site's designated unblinded investigational product manager is required to maintain accurate investigational product accountability records. Upon completion of the study, copies of investigational product accountability records will be returned to MedImmune. All unused investigational product will be returned to a MedImmune-authorized depot or disposed of upon authorization by MedImmune.

4.6 Treatment Assignment and Blinding

4.6.1 Methods for Assigning Treatment Groups

An IXRS will be used for randomization to a treatment group and assignment of investigational product kit numbers if assigned to an active treatment arm. A subject is considered randomized into the study when the investigator notifies the IXRS that the subject

meets eligibility criteria and the IXRS provides the assignment of treatment group and allocates active treatment if assigned to the active treatment arm.

Subjects will be randomized in a 4:1 ratio (Cohort 1), in a 5:2 ratio (Cohort 2), in a 3:1 ratio (Cohort 3), and in a 5:2 ratio (Cohort 4) to receive either MEDI4920 or placebo respectively as described in Table 3.1.2-1.

Investigational product (MEDI4920 or placebo) must be administered the same day the investigational product is assigned. If there is a delay in the administration of investigational product such that it will not be administered within the specified timeframe, the study monitor must be notified immediately.

4.6.2 Methods for Ensuring Blinding

This is a double-blind study in which MEDI4920 and the saline placebo are not identical in appearance. As such, neither the subject/legal representative nor any of the investigator or sponsor staff who are involved in the treatment or clinical evaluation of the subjects will be aware of the treatment received (ICH E9) (see Section 4.6.4 for unblinding related to interim analysis). For maintaining the blinding of the principal investigator, site staff, sponsor, Contract Research Organization (CRO) or staff, a local unblinded pharmacy staff member will be nominated by each site and will have the responsibility of allocating, dispensing and preparing the investigational product in order to maintain the study blind. In addition, a separate unblinded monitor will be used for the oversight of investigational product management. If treatment allocation for a subject becomes known to the investigator or other study staff involved in the management of study subjects, the sponsor must be notified *immediately*.

4.6.3 Methods for Unblinding

4.6.3.1 Unblinding in the Event of a Medical Emergency

In the event of a medical emergency, the investigator may unblind an individual subject's investigational product allocation. Instructions for unblinding an individual subject's investigational product allocation are contained in the IXRS manual. In general, unblinding should only occur if management of the medical emergency would be different based on the subject having received investigational product. In the majority of cases, the management of a medical emergency would be the same whether or not investigational product was received by the subject. If this was the case, the investigational product allocation should not be unblinded.

4.6.4 Unblinding for Interim Analysis Purposes

The primary analysis will be performed when all subjects in Cohort 3 have completed the Day 85 assessments or have been withdrawn from the study. The primary analysis will include all assessments on the subjects prior to the data cut-off for the primary analysis.

MedImmune personnel will be unblinded to the subject treatment assignments from Cohorts 1 to 3 at the primary analysis (Day 85). The data from the primary analysis will not be communicated to personnel at the CRO or investigational sites or to enrolled subjects, until all subjects in Cohorts 1 to 3 have completed the study and database lock has been achieved.

MedImmune personnel will be unblinded for Cohort 4, and the data will be analyzed when all subjects in Cohort 4 have completed the Day 85 assessments or have been withdrawn from the study. Study subjects and personnel at the CRO or investigational sites will remain blinded to Cohort 4 data until all subjects in Cohort 4 have completed the study and database lock has been achieved.

The final analysis on the subjects will be performed when all subjects have completed the safety follow-up.

4.7 Restrictions During the Study and Concomitant Treatment(s)

The investigator must be informed as soon as possible about any medication taken from the time of screening until the end of the clinical phase of the study (final study visit). Any concomitant medication(s), including over-the-counter products (and any herbal supplements), taken during the study will be recorded in the eCRF.

4.7.1 Permitted Concomitant Medications

Investigators may prescribe concomitant medications or treatments deemed necessary to provide adequate supportive care except for those medications identified as "excluded" as listed in Section 4.7.2. Specifically, subjects should receive full supportive care during the study, including transfusions of blood and blood products, and treatment with antibiotics, anti-emetics, anti-diarrheals, and analgesics, and other care as deemed appropriate, and in accordance with their institutional guidelines.

4.7.2 **Prohibited Concomitant Medications**

Subjects must refrain from alcohol consumption for 48 hours prior to all visits.

Subjects must refrain from strenuous exercise for approximately 48 hours before each study day where safety samples will be taken, and Day 169/EDV. Physical therapy including cold/hot applications, electrical stimulation, and hydrotherapy, applied specifically for RA, is not permitted between Days 1 and 85.

The introduction of the following medications is not permitted from initiation of screening through to the end of the study. The sponsor must be notified if any of the following medications are given to a subject during the study (with the exception of stable doses of DMARDs permitted prior to screening/randomization as applicable):

- 1. Investigational drug therapy other than MEDI4920
- 2. Biologic DMARD therapies (such as anti-TNF, recombinant IL-1 receptor antagonist, anti-IL-6, CTLA-4 Ig, B-cell depleting therapies, etc) or JAK inhibitors.
- 3. Mycophenolate mofetil, cyclophosphamide, and other alkylating agents
- 4. Live (attenuated) vaccine. Immunization with any live or live attenuated vaccine (ie, measles, mumps, rubella and polio vaccine, Bacillus Calmette-Guerin, typhoid, yellow fever, cold adapted live influenza strain vaccine, or any other vaccines not yet licensed but belonging to this category) is specifically excluded during the treatment period (ACIP, 2011).
- 5. Immunoabsorption columns, total lymphatic irradiation, plasmapheresis and IV immunoglobulin therapy

After Day 85, the dose of background cDMARDs and corticosteroids may be adjusted or a new additional cDMARD may be added to an existing one (except for combining MTX and leflunomide) if it is clinically indicated to improve disease management.

Subjects must be instructed not to take any medications or over-the-counter products (including herbal supplements), without first consulting with the investigator.

4.8 Statistical Evaluation

4.8.1 General Considerations

Tabular summaries will be presented by treatment group. Categorical data will be summarized by the number and percentage of subjects in each category. Continuous variables will be summarized by descriptive statistics. Additional details of statistical analyses will be described in the statistical analysis plan.

The intent-to-treat (ITT) population is defined as all subjects who are randomized and receive any amount of investigational product. Subjects will be analyzed by the randomized

the sample sizes of 14,

treatment group. All efficacy and biomarker analyses will be performed on the ITT population unless otherwise specified.

The as-treated population is defined as all subjects who are randomized and treated with investigational product. Subjects will be analyzed by the treatment received. All safety analyses will be performed on the As-Treated population unless otherwise specified.

4.8.2 Sample Size and Power Calculations

No formal sample size calculations are presented for the evaluation of the primary objective of safety and tolerability of MEDI4920. The sample size calculations are based on the exploratory endpoint ^{CCI}

The sample size calculation for the change from baseline in DAS28 CRP at Week 12 is based on combining the data from the cohorts and performing a dose response analysis. Based on the assumption ^{CCI}

8, 10, 10 and 12 subjects for the placebo, 75, 500, 1000 and 1500 mg dose groups, respectively, will provide approximately 92% power for detecting a statistically significant dose response, using a significance level of 0.10.

The power for dose response has been calculated using a multiple comparison procedure with modeling techniques (MCP-Mod; Bretz et al, 2005), with three candidate models for the dose response (linear, maximum effect attributable to the drug $[E_{max}]$, and a Hill- E_{max} model). An overall significance level of 0.10 will be used to test for dose response.

4.8.3.1

4.8.3 **Exploratory Efficacy Analyses**

4.8.4 Safety

4.8.4.1 Analysis of Adverse Events

AEs will be coded using the Medical Dictionary for Regulatory Activities (MedDRA) by system organ class (SOC) and preferred term (PT). Specific AEs will be counted once for each subject for calculating rates, but will be presented in total in subject listings. In addition, if the same AE occurs multiple times within a particular subject, the highest severity and level of causality will be reported. If any associations of interest between AEs and baseline characteristics are observed, additional stratified results may be presented. All TEAEs will be summarized overall and by MedDRA SOC and PT, and by severity and relationship to investigational product. In addition, summaries of deaths, SAEs and treatment discontinuations due to AEs will be provided. TEAEs, treatment-emergent SAEs (TESAEs) and AESIs with onset after the start of infusion (Day 1) to Day 169/EDV inclusive will be summarized by dose. The placebo subjects from each cohort will be combined for the summaries.

Other safety parameters, including laboratory assessments and vital signs, will be summarized by dose.

4.8.4.2 Analysis of Clinical Laboratory Parameters

Laboratory parameters will be assessed at baseline as well as throughout the study. Frequencies of abnormal laboratory measurements will be presented for each laboratory parameter. Also, laboratory parameters will be assessed by presenting tables containing information related to laboratory shifts from baseline relative to the normal range, as well as descriptively over time.

4.8.4.3 Other Safety and Tolerability Endpoints

Other safety parameters, including vital signs and ECGs, will be summarized by dose and time point.

4.8.5 Analysis of Immunogenicity/Pharmacokinetics

The number and percentage of subjects who develop detectable ADA will be summarized by dose. The impact of ADA on PK and the association with AEs and SAEs will be assessed. Plasma MEDI4920 concentration data at each time point will be tabulated by dose cohort together with descriptive statistics. Individual and mean plasma concentration-time profiles of MEDI4920 by dose cohort will be generated. Non-compartmental PK data analysis will be performed and descriptive statistics for PK parameters will be provided.

4.8.6 Interim Analysis

The primary analysis will be performed when all subjects in Cohort 3 have completed the Day 85 assessments or have been withdrawn from the study. The primary analysis will include all assessments on the subjects prior to the data cut-off for the primary analysis.

MedImmune personnel will be unblinded to the subject treatment assignments from Cohorts 1 to 3 at the primary analysis (Day 85). The data from the primary analysis will not be communicated to personnel at the CRO or investigational sites or to enrolled subjects, until all subjects in Cohorts 1 to 3 have completed the study and database lock has been achieved. An additional interim analysis will be performed when all subjects in the Cohort 4 have completed the Day 85 assessments or have been withdrawn from the study. MedImmune personnel will be unblinded to the subject treatment assignments from Cohort 4 for this interim analysis. Study subjects and personnel at the CRO or investigational sites will remain blinded to Cohort 4 data until all subjects in Cohort 4 have completed the study and database lock has been achieved.

The final analysis on the subjects will be performed when all subjects have completed the safety follow-up.

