AEs will be coded using the Medical Dictionary for Regulatory Activities (MedDRA) by system organ class (SOC) and preferred term (PT). Specific AEs will be counted once for each subject for calculating rates, but will be presented in total in subject listings. In addition, if the same AE occurs multiple times within a particular subject, the highest severity and level of causality will be reported. If any associations of interest between AEs and baseline characteristics are observed, additional stratified results may be presented. All treatment-emergent AEs will be summarized overall and by MedDRA SOC and PT, by severity, and by relationship to investigational product. In addition, summaries of deaths, SAEs and treatment discontinuations due to AEs will be provided. Treatment-emergent AEs, treatment-emergent SAEs and AESIs with onset after the start of infusion (Day 1) to Day 169/Early Discontinuation Visit inclusive will be summarized by dose. The placebo subjects from each cohort will be combined for the summaries. Other safety parameters, including laboratory assessments and vital signs, will be summarized by dose.

Interim Analysis:

The primary analysis will be performed when all subjects in Cohort 3 have completed the Day 85 assessments or have been withdrawn from the study. The primary analysis will include all assessments on the subjects prior to the data cut-off for the primary analysis. MedImmune personnel will be unblinded to the subject treatment assignments from Cohorts 1 to 3 at the primary analysis (Day 85). The data from the primary analysis will not be communicated to personnel at the Contract Research Organization (CRO) or investigational sites or to enrolled subjects, until all subjects in Cohorts 1 to 3 have completed the study and database lock has been achieved. An additional interim analysis will be performed when all subjects in Cohort 4 have completed the Day 85 assessments or have been withdrawn from the study. MedImmune personnel will be unblinded to the subject treatment assignments from Cohort 4 for this interim analysis. Study subjects and personnel at the CRO or investigational sites will remain blinded to Cohort 4 data until all subjects in Cohort 4 have completed the study and database lock has been achieved. The final analysis on the subjects will be performed when all subjects have completed the safety follow-up.

TABLE OF CONTENTS

PRO	тосс	DL SYNOPSIS	2	
LIST	OF A	ABBREVIATIONS	10	
1	INT	RODUCTION	13	

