3.1.2 Treatment Regimen

A maximum of 54 subjects will be randomized in a 4:1 ratio (Cohort 1), in a 5:2 ratio (Cohort 2), in a 3:1 ratio (Cohort 3), and in a 5:2 ratio (Cohort 4) to receive either MEDI4920 or placebo as described in Table 3.1.2-1:

Cohort	N (active:placebo)	Dose	Treatment Regimen ^a
1	4:1	75 mg	Single IV dose infused over at least 30 minutes on Days 1, 15, 29, 43, 57, 71, and 85
2	5:2	500 mg	Single IV dose infused over at least 60 minutes on Days 1, 15, 29, 43, 57, 71, and 85
3	3:1	1500 mg	Single IV dose infused over at least 90 minutes on Days 1, 15, 29, 43, 57, 71, and 85
4	5:2	1000 mg	Single IV dose infused over at least 90 minutes on Days 1, 15, 29, 43, 57, 71, and 85

Table 3.1.2-1 Investigational Product Dose and Treatment Regimen

IV = intravenous; TBD = to be determined.

^a For Cohorts 1-4, investigational product will be administered via IV infusion using an IV infusion pump.

The timing of administration of investigational product will be staggered within each cohort to allow for review of safety and tolerability data from the first group of subjects before progression to the next group of subjects.

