3.1.3 Dose Escalation and Cohort Progression

Cohorts 1 to 3 will start sequentially, with escalation from Cohort 1 to Cohort 2 and Cohort 2 to Cohort 3 confirmed by a Dose Escalation Committee (DEC) comprised of MedImmune study team members and the Study Global Chief Investigator, who will assess in a blinded fashion the safety/tolerability data after the last subject in a cohort completes Day 29 (Week 4) of treatment and has AE/safety laboratory data available at that time point. There will be a total of three DEC meetings during the study; the first DEC meeting will only review data from Cohort 1 whereas the second DEC meeting will review cumulative safety data from first two dose cohorts being tested to date. The third DEC meeting will constitute a thorough evaluation of the cumulative safety and tolerability data for Cohorts 1 and 2 in addition to the data up to Day 85 for Cohort 3. While this review will not pertain to a dose escalation, it will contribute to the decision to instigate Cohort 4 (see below).

After the last Cohort 3 subject completes the Day 85 (Week 12) assessments, the primary analysis will be conducted to include safety, tolerability, PK, ADA, biomarker, and clinical response. Based on the outcome of this analysis, a fourth cohort will be included to better understand the dose (exposure)-response relationship.

If one or more of the following criteria are met, dose escalation will be suspended and the event(s) will be fully evaluated:

- A subject dosed with MEDI4920 experiences a confirmed or suspected thromboembolic event during the evaluation period or follow-up period. If the thromboembolic event is initially reported as "suspected", because of the unavailability of sufficient information to support a definitive diagnosis at that time, the DEC will re-assess the event when complete clinical/laboratory information is provided by the study site. A diagnosis algorithm (adapted from Wells and Anderson, 2013; Section 10.5 [Appendix 5]), is recommended to be used for any case of suspected DVT or PE. This includes clinical pre-test probability, D-dimer, and available imaging results. Based on full evaluation of the data as well as the diagnosis algorithm, if a thromboembolic event is ruled out or considered unlikely, dose escalation can be resumed.

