6.3 Study Timetable and End of Study

An individual subject will be considered to have completed the study if the subject was followed through the last protocol-specified visit/assessment (including telephone contact), regardless of the number of doses of investigational product that was received.

Subjects will be considered not to have completed the study if consent was withdrawn or the subject was lost to follow-up (see Section 4.1.5 and Section 4.1.6).

The end of the study ("study completion") is defined as the date of the last protocol-specified visit/assessment (including telephone contact) for the last subject in the study.

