7.5 Changes to the Protocol and Informed Consent Form

Study procedures will not be changed without the mutual agreement of the principal investigator and MedImmune.

If there are any substantial changes to the study protocol, then these changes will be documented in a study protocol amendment and where required in a new version of the study protocol.

The amendment is to be approved by the relevant IRB/IEC and if applicable, also the national regulatory authority, before implementation. Local requirements are to be followed for revised protocols.

MedImmune will distribute any subsequent amendments and new versions of the protocol to each principal investigator(s). For distribution to the IRB/IEC see Section 7.3.

If a protocol amendment requires a change to a site's ICF, MedImmune and the site's IRB/IEC are to approve the revised ICF before the revised form is used.

If local regulations require, any administrative change will be communicated to or approved by each IRB/IEC.

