2.3 Treatment Assignment and Blinding

An interactive voice/web response system (IXRS) will be used for randomization to a treatment group and assignment of investigational product kit numbers if assigned to an active treatment arm. A subject is considered randomized into the study when the investigator notifies the IXRS that the subject meets eligibility criteria and the IXRS provides the assignment of treatment group and allocates active treatment if assigned to the active treatment arm.

Subjects will be randomized in a 4:1 ratio (Cohort 1), in a 5:2 ratio (Cohort 2), in a 3:1 ratio (Cohort 3), and in a 5:2 ratio (Optional Cohort 4) to receive either MEDI4920 or placebo respectively.

This is a double-blind study in which MEDI4920 and the saline placebo are not identical in appearance. For maintaining the blinding of the principal investigator, site staff, sponsor, Contract Research Organization (CRO) or staff, a local unblinded pharmacy staff member will be nominated by each site and will have the responsibility of allocating, dispensing and preparing the investigational product in order to maintain the study blind. In addition, a separate unblinded monitor will be used for the oversight of investigational product management.

MedImmune personnel will be unblinded to the subject treatment assignments at the primary analysis (Day 85). The data from the primary analysis will not be communicated to personnel at the CRO or investigational sites or to enrolled subjects, until the study is complete.

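### Protocol and SAP set different release points for the unblinded Cohort 1-3 results, and the protocol's could fall before Cohort 4's Week 12 visits; the SAP's design, power and interim text also predates Amendment 3

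*Protocol*

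**What the plan says.** **Release of the Cohort 1-3 results.** The sponsor is unblinded to Cohorts 1-3 at the primary analysis. Protocol 4.8.6 keeps the results from the CRO, sites and subjects "until all subjects in Cohorts 1 to 3 have completed the study and database lock has been achieved". Section 4.6.4 uses the same condition, "all subjects in Cohorts 1 to 3 have completed the study and database lock has been achieved", and the synopsis repeats the embargo ("The data from the primary analysis will not be communicated to personnel at the Contract Research Organization (CRO) or investigational sites") with the same end point. A separate sentence keeps the CRO, sites and subjects blinded to Cohort 4 data until Cohort 4 has completed and locked.

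SAP 2.3 words the embargo differently. The results stay from CRO personnel and from "investigational sites or to enrolled subjects, until the study is complete". Protocol 6.3 says that study completion "is defined as the date of the last protocol-specified visit/assessment (including telephone contact) for the last subject in the study".

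**When Cohort 4 starts.** Protocol 3.1.3 places it after the primary analysis: "Based on the outcome of this analysis, a fourth cohort will be included". Section 7.5 adds "The amendment is to be approved by the relevant IRB/IEC and if applicable, also the national regulatory authority, before implementation". Section 3.1.2 adds "The timing of administration of investigational product will be staggered within each cohort".

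**Design text.** Protocol 4.8.2 gives five groups and 92% power, 3.1.1 fixes the Cohort 4 regimen, and 4.8.6 names an additional interim analysis at Cohort 4 Day 85. SAP 2.4 gives four groups and 80% power, SAP 2.2 treats Cohort 4 as optional with infusion duration and frequency still open, and SAP Section 4 states that there are no interim analyses.

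**The concern.** Site staff or subjects who know how the earlier doses performed may score Cohort 4 with that in mind. Two components are open to this: the patient global, which enters DAS28 CRP and CDAI, and the physician global, which enters CDAI. Cohort 4 data are pooled with Cohorts 1-3 for the dose-response analysis, and Protocol 3.2.1 explains Cohort 4 by reference to the response at 1500 mg. An expectation effect confined to Cohort 4 would therefore bear on comparisons across cohorts.

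The second stake is plainer. An SAP left as it stands gives a sample size and power for a design that is no longer the trial's.

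**Working it through.** **1. Can release come before Cohort 4 Week 12?** Count days from the last Cohort 3 Day 85 visit.

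Inputs: Day 85 ±1 (Protocol 4.2.2), Day 169 ±3 (4.2.3), and screening from Day -42 to Day -1, so 1 to 42 days before Day 1 (4.2.1). Assumed, because the documents do not give it: A days for analysis, decision and approval.

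- Cohorts 1-3 complete: 169 − 85 = 84 days nominal; 84 ± 4 = +80 to +88 with windows.
- First Cohort 4 Day 85: A + (1 to 42) + (83 to 85).
- Time available for lock: earliest Cohort 4 date minus 88, to latest minus 80.

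| A (assumed) | First Cohort 4 Day 85 | Lock must take less than |
|---|---|---|
| 0 days | +84 to +127 | −4 to 47 days |
| 30 days | +114 to +157 | 26 to 77 days |
| 60 days | +144 to +187 | 56 to 107 days |

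A lock within the last column would permit release before every Cohort 4 Week 12 visit. A somewhat later lock would still precede the visits of subjects enrolled later.

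**2. How far apart are the two rules?** Under SAP 2.3 the earliest possible date has A = 0, one day of screening and no enrolment time: 1 + (168 − 3) = +166. Against the latest Cohort 1-3 completion, 166 − 88 = 78 days. Any real analysis, approval and enrolment time adds to this.

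**3. What could an expectation effect do?** The patient global has weight 0.014 in DAS28 CRP (Protocol 4.3.6.4). Assume a shift of 10 to 20 mm in all 14 Cohort 4 subjects: 0.014 × 10 = 0.14 and 0.014 × 20 = 0.28 units.

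- 1000 mg against Cohort 4's own 4 placebo subjects: both sides shift, so 0.
- 1000 mg against the 14 pooled placebo subjects: shift × (1 − 4/14) = 0.10 to 0.20.
- 1000 mg against 1500 mg: the whole shift, 0.14 to 0.28.
- Pooled MCP-Mod test: simulated with groups of 14/8/10/10/12 and no cohort term, two-sided at 0.10, with assumed SDs of 1.0 to 1.5 and five assumed sets of candidate shapes (the plan's own are redacted). The false-positive rate was 0.099 to 0.106 against 0.10.

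**4. Sample size and power.** Placebo: 2 + 4 + 4 = 10 in the SAP; adding Cohort 4's 4 gives 14 in the protocol. Totals: 10 + 8 + 10 + 12 = 40 and 14 + 8 + 10 + 10 + 12 = 54. Neither 80% nor 92% can be reproduced, because the effect size and SD are redacted. As a consistency check, effects set to give 80% at 40 subjects gave 86.5% to 91.3% at 54 over six assumed sets of candidate models, one- and two-sided. The top of that range is close to 92%.

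**The case against.** - **The protocol sets an embargo and schedules no release.** This stands. The finding is that early release is permitted.
- **The lock might mean a single study-level lock,** in which case early release could not occur. Neither document defines a separate Cohort 1-3 lock. The reading is strained, though, because the protocol gives Cohort 4 its own completion-and-lock condition. The ambiguity is itself a reason to settle the wording.
- **The efficacy scores are well protected.** Largely true. Cohort 4 allocation stays blinded, joint counts come from an independent blinded assessor (Protocol 4.3.6.1), and CRP is a laboratory value. All of this concerns exploratory endpoints in a trial whose primary objective is safety.
- **The assumed shift is a worst case.** Also fair. The endpoint is change from baseline, so for a subject enrolled after release a constant shift affects Day 1 as well and cancels. Sites can already read in Protocol 3.2.1 that 1000 mg is expected to perform like 1500 mg, so release only adds to an existing expectation. Cohorts 3 and 4 are also sequential, so drift between them exists under either rule.
- **The SAP mismatch is version lag.** Partly. The SAP already has Cohort 4 at 10 active and 4 placebo, and its Section 4 plans the Cohort 4 Day 85 analysis, so the statement on interim analyses is mainly a label. The group sizes, power and undetermined regimen are real differences in current text.

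**Conclusion.** The conflict holds in the current text of both documents. They give different end points for the same embargo, and following the protocol's could breach the SAP's by 78 days or more. Whether release would in fact precede Cohort 4 Week 12 depends on lock, approval and start dates that the documents do not give; the 26 to 77 days rest on the assumed 30.

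The consequence is limited to the patient and physician global scores, in exploratory endpoints, where Cohort 4 is set against earlier cohorts. The comparison with Cohort 4's own placebo is not affected by a shift common to that cohort.

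Three stronger readings are not supported:

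- A reader might infer that Cohort 4 would be unblinded or the dose-response test invalidated. Allocation stays concealed, and the simulated error rate barely moves.
- A reader might turn the 0.14 to 0.28 into a probability of misjudging 1000 mg against 1500 mg. That needs an assumed size, direction and SD, in a comparison that no visible passage plans.
- A reader might infer that the 92% is wrong. The inputs are redacted and the check does not contradict it. What is shown is that 80% and 92% describe different designs.

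The change is worth making because it is cheap and removes an avoidable source of bias; the trial's primary conclusions do not turn on it.

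**What to change.** 1. Use one release rule in Protocol 4.6.4, 4.8.6 and the synopsis and in SAP 2.3: no Cohort 1-3 results to the CRO, sites or subjects until Cohort 4 has completed the study and its database is locked. This keeps the later release point of SAP 2.3 and adds the lock condition, which SAP 2.3 lacks. Emergency unblinding (Protocol 4.6.3.1) is unaffected.
2. Update SAP 2.2, 2.4 and 4: five groups of 14/8/10/10/12, the protocol's 92% power, the Cohort 4 Day 85 interim by name, and a Cohort 4 description reconciled with the protocol.

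The cost is wording in two documents, with no new subjects, visits or data. Sites wait longer for Cohort 1-3 results: at least about 78 days, taking lock times as similar, plus the time for analysis, approval and Cohort 4 enrolment.
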